## Appendix 2. Definition of Topical and Systemic Atopic Dermatitis Therapy

---

The atopic dermatitis rescue therapy in this study is defined as: high-potency topical corticosteroid (TCS) and systemic atopic dermatitis therapy. The topical treatments and systemic treatments are defined as following:

### 1. Topical Atopic Dermatitis Treatment (including topical corticosteroids, topical calcineurin inhibitors [TCIs], and crisaborole)

Route of topical treatment includes: Topical or Transdermal

Topical Corticosteroids (TCS): Anatomical Therapeutic Chemical (ATC) code is D07

High-Potency TCS: ATC codes: D07AC or D07AD

Low or Moderate-Potency TCS: ATC code is D07, excluding D07AC or D07AD

TCI: Preferred Term includes: TACROLIMUS and PIMECROLIMUS

Crisaborole: Preferred Term includes: CRISABOROLE

### 2. Systemic Atopic Dermatitis Treatment (including systemic corticosteroids, immunosuppressant, biologics and phototherapy/photochemotherapy)

Route of systemic treatments administration includes: Oral, Intra-Arterial, Intramuscular, Intraperitoneal, Intravenous, Subcutaneous, and Transdermal. (This condition applies to the following categories except for phototherapies.)

Systemic Corticosteroids: ATC code is H02.

Immunosuppressant: Defined as: ATC2 is L04 or Preferred Terms (PTs) of Abrocitinib or Ruxolitinib.

Biologics: Defined as following PTs:

- Infliximab, Infliximabum, Etanercept, Etanerceptum, Adalimumab, Adalimumabum, Certolizumab, Certolizumabum, Certolizumab pegol, Golimumab, Golimumabum, Ozoralizumab, Afelimomab, Afelimomabum, Tumor Necrosis Factor Alpha (TNF-) Inhibitors, Tabalumab, Tregalizumab, Anakinra, Basiliximab, Basiliximabum, Daclizumab, Daclizumabum, Tocilizumab, Tocilizumabum, Mepolizumab, Mepolizumabum, Rilonacept, Rilonaceptum, Ustekinumab, Canakinumab, Briakinumab, Fezakinumab, Sirukumab, Sarilumab, Lebrikizumab, Secukinumab, Olokizumab, Gevokizumab, Brodalumab, Ladarixin, Ixekizumab, Dupilumab, Tildrakizumab, Tildrakizumabum, Reslizumab, Reslizumabum, Guselkumab, Guselkumabum, Olamkicept, Fletikumab, Bimekizumab, Mirikizumab, Risankizumab, Abatacept, Ligelizumab, Vedolizumab, Belimumab, Nemolizumab, Tralokinumab, Omalizumab

Phototherapy or Photochemotherapy:

If the programming search of the medication name (actual term or PT) contains 'photo,' then medical is to manually review to confirm whether the medication in question is indeed 'Phototherapy' or 'Photochemotherapy.'

---

## Appendix 3. Details of Combining Estimates and Test Statistics for Categorical Endpoints with Multiple Imputation

---

Following the implementation of Markov Chain Monte Carlo multiple imputation (MCMC-MI) imputation as specified in Section 6.4.1, the 25 data sets with imputations should be set together and sorted by imputation number. The following sections describe the processes for combining inferences for the individual imputed data sets into 1 inference for reporting. All calculations are performed in SAS software version 9.4.

### **Summarize Unadjusted Response Rate**

The response rates, overall and by treatment arm, and their associated standard errors (SEs) are computed for each imputed data set using PROC FREQ with the *riskdiff* option specified for the appropriate column in the TABLES statement. The response rates and SEs from the resulting output are combined across the 25 imputed data sets using PROC MIANALYZE, separately for each arm and the overall group.

Note that the estimate and 95% confidence interval (CI) bounds output by PROC MIANALYZE are percents (that is, they are in terms of the response rate). To obtain the number of responders, the estimated percent is multiplied by the number of individuals in the analysis population and rounded to the nearest integer.

### **Compute Stratified Measures of Association**

The common risk difference, common odds ratio (OR), and Cochran-Mantel-Haenszel (CMH) test statistic are computed for each imputed data set using PROC FREQ with the *riskdiff* option for the appropriate column (for risk difference) and the *cmh* option (for odds ratio and CMH test statistic) specified in the TABLES statement. Each of these analyses are stratified by geographic region, age group, and baseline disease severity via inclusion of these variables in the TABLES statement with the treatment and outcome variables.

Note that the PROC FREQ output corresponding to the Mantel-Haenszel method is used for the risk difference, and the output corresponding to the General Association statistic is used for the CMH statistic. PROC MIANALYZE is then called separately for each of these measures, with further details in the sections below.

#### **Common Risk Difference**

No transformation is necessary before using PROC MIANALYZE to combine the risk difference estimates and their associated SEs across the 25 imputed data sets. This procedure outputs an estimate of the common risk difference and the associated 95% CI bounds.

#### **Common Odds Ratio**

The OR from each imputed data set is first transformed using the natural logarithm. The SE for each log OR ( $SE_{IOR}$ ) is derived from the OR 95% CI bounds ( $LB_{OR}$ ,  $UB_{OR}$ ) according to the following equation:  $SE_{IOR} = (\ln(UB_{OR}) - \ln(LB_{OR})) / (2 * 1.96)$ . The log OR and derived SE are then combined using PROC MIANALYZE, which outputs a combined estimate of the log OR and the associated 95% CI. Finally, these measures can be exponentiated to transform them back to the OR scale.

### CMH Test

The CMH test statistic ( $CMH$ ) from each imputed data set is transformed using the Wilson-Hilferty transformation and standardized so that it has approximately a standard normal distribution (Ratitch 2013). In particular, the transformed CMH statistic is computed as follows:

$$CMH_{WH} = \frac{\left(\frac{CMH}{df}\right)^{\frac{1}{3}} - \left(1 - \frac{2}{9 * df}\right)}{\sqrt{\frac{2}{9 * df}}}$$

where  $df$  is the degrees of freedom of the CMH statistic. Then the SE for each  $CMH_{WH}$  is 1, and PROC MIANALYZE is used to output a combined estimate of the transformed CMH statistic. Note that the 2-sided p-value output by PROC MIANALYZE is not used directly, but instead the 1-sided p-value is computed manually using both the t statistic and 2-sided p-value output by PROC MIANALYZE; if t statistic is >0, then the 1-sided p-value is computed as one half of the 2-sided p-value; otherwise, the 1-sided p-value is computed as one half of the 2-sided p-value. The resulting 1-sided p-value is reported as the pooled p-value for the CMH test.

Leo Document ID = e0255821-6fc0-46ae-83e9-32466b82a78f

PPD

Approval Date & Time: 15-Oct-2021 18:41:01 GMT

Signature meaning: Approved

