5.3. Patient Randomization

Patients will be assigned a unique identifier by the sponsor. Any patient records, datasets or tissue samples that are transferred to the sponsor will contain the identifier only; patient names or any information which would make the patient identifiable will not be transferred. All patients will be randomly allocated to receive the study treatment using an electronic data capture system (an electronic randomization and trial supply management system) at the Baseline visit. The allocation to treatment will be prospectively stratified by geographic region (US versus EU versus rest of world), age (adolescent patients 12 to <18 years versus adults ≥18 years) and disease severity (IGA 3 versus 4). At the Baseline visit (Day 1), once a patient is considered eligible to participate in the study, demographic and stratification information will be entered into the EDC to receive a medication number assigning the appropriate treatment to a patient. Patients will be randomized 2:1 to one of the following treatment groups:

- Lebrikizumab 250mg Q2W: 500mg lebrikizumab administered at Baseline and Week 2 (loading dose) and 250mg given every two weeks (Q2W) through Week 14. TCS treatment initiated at Baseline and applied PRN.
- Placebo 4mLs (two PFS-NSD) administered at Baseline and Week 2 and 2mLs given Q2W through Week 14. TCS treatment initiated at Baseline and applied PRN.

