## 6. A Priori Statistical Methods

### 6.1. General Considerations

Statistical analysis of this study will be the responsibility of Eli Lilly and Company (Lilly). The latest version of the Medical Dictionary for Regulatory Activities (MedDRA) will be used.

Analyses and summaries from assessment of endpoints described in the protocol (for example, described in KGAD Protocol Table 1) are planned to be included in a clinical study report (CSR). Analyses and summaries for key safety data are also planned to be included in the CSR. Results from additional efficacy analysis and other safety analyses may also be provided in the CSR as deemed appropriate.

Any change to the data analysis methods described in the protocol will require a protocol amendment ONLY if it changes a principal feature of the protocol. Any other change to the data analysis methods described in the protocol and the justification for making the change will be described in the CSR.

All statistical processing will be performed using SAS® unless otherwise stated. Some of the analyses described in this document will be incorporated into interactive display tools instead of or in addition to static displays. Except where noted, all statistical tests will be two-sided and will be performed at the 0.05 level of significance.

The Schedule of Visits and Procedures outlined in the protocol specifies the allowable windows for assessments. Assessments performed outside these windows will not be excluded from any analysis, unless specified otherwise.

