### **6.6. Multiple Comparisons/Multiplicity**

#### **6.6.1. Multiplicity Control for US Submission**

A pre-specified graphical multiple testing approach (Bretz et al. 2009, 2011) will be implemented to control the overall Type I error rate at a 2-sided alpha of 0.05, for all primary and major secondary endpoints for US submission. A gatekeeping approach will be used for multiple comparisons to control the family-wise error rate.

The following is a list of primary and major secondary endpoints to be tested in sequential order for US submission.

[figure not shown]

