### **6.11.1. Primary Outcome and Methodology**

The primary analysis of the study is to test the null hypotheses that lebrikizumab 250 mg Q2W is the same as placebo when evaluating the proportion of patients achieving IGA of 0 or 1 at Week 16 in the mITT Population. For EMA, an additional null hypothesis is that lebrikizumab 250 mg Q2W is the same as placebo when evaluating the proportion of patients achieving EASI-75 at Week 16 in the mITT Population.

The primary estimand for the primary analysis is described in Section 6.2.1. The missing values will be imputed using MCMC-MI based on missing at random assumption (Section 6.4.1).

A CMH test as described in Section 6.1.2 will be used for the comparisons. The odds ratio, the corresponding 95% CIs and p-value, as well as the treatment differences and the corresponding 95% CIs, will be reported.

Multiplicity controlled analyses will be performed on the primary and major secondary objectives to control the overall Type I error rate at a 2-sided alpha level of 0.05. A gatekeeping approach will be used to perform the multiplicity controlled analyses as described in Section 6.6.

Primary outcome IGA 0/1 and EASI-75 and their analysis are described in [Table KGAD.6.8](#) and [Table KGAD.6.9](#).

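### The pooled CMH p-value in SAP Appendix 3 applies a Wilson-Hilferty transform to a 1-df statistic, which makes the nominal 5% test slightly anti-conservative (asymptotic size 5.29%)

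*SAP*

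**What the plan says.** SAP 6.1 states that, except where noted, "all statistical tests will be two-sided and will be performed at the 0.05 level of significance". SAP 6.6.1 uses a graphical gatekeeping scheme to "control the overall Type I error rate at a 2-sided alpha of 0.05, for all primary and major secondary endpoints for US submission", and 6.6.2 makes the same commitment for the EU submission.

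For the primary outcome, SAP 6.11.1 says "A CMH test as described in Section 6.1.2 will be used for the comparisons". Missing data are handled with 25 imputed data sets (SAP 6.4.1). Appendix 3 gives the pooling steps:

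- In each imputed data set, "the output corresponding to the General Association statistic is used for the CMH statistic".
- That statistic is put through the Wilson-Hilferty transform and "standardized so that it has approximately a standard normal distribution".
- Each transformed value is given standard error 1, and "PROC MIANALYZE is used to output a combined estimate of the transformed CMH statistic".
- The one-sided p-value derived from that output is reported as the pooled CMH p-value.

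The SAP does not print the degrees of freedom. They follow from the design. Protocol 5.3 says "Patients will be randomized 2:1 to one of the following treatment groups" and lists two groups, and the response is binary, so df = (2 − 1)(2 − 1) = 1.

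**The concern.** The Wilson-Hilferty transform turns a chi-square variable into an approximately normal one, and the approximation improves as the degrees of freedom rise. Here it is used at 1 df, and the SAP gives no check of it there. If the approximate normal tail is lighter than the true chi-square tail near the working significance level, the reported p-values are too small.

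What is at stake is the calibration of the p-value that opens both gatekeeping schemes. All five US endpoints in SAP 6.6.1 are binary and use this route. So do six of the ten EU endpoints in 6.6.2: IGA 0/1, EASI-75, EASI-90, Pruritus NRS-4, the EASI-75 and Pruritus composite, and the DLQI responder endpoint. A graphical procedure controls the family-wise error rate strongly only if each component test holds its own level.

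The plan would also apply two yardsticks to one statistic. The nonresponder-imputation analyses have a single data set and use the ordinary CMH p-value (critical value 3.841). The imputed analyses in effect use 3.747.

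**Working it through.** **Inputs.** Two-sided alpha 0.05 (SAP 6.1, 6.6). df = 1 (derived above). 25 imputations (SAP 6.4.1). 225 patients at 150:75, with assumed IGA 0/1 rates of 38% and 13% and EASI-75 rates of 58% and 20% (SAP 5.2). The documents give no missing-data rate, so 0 to 20% is assumed. Stratum sizes are also assumed, across the planned 3 × 2 × 2 = 12 strata.

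**The plan's own figure.** SAP 5.2 states power above 95% with a two-sided Fisher's exact test. Exact enumeration gives 98.4% for IGA 0/1 and 99.99% for EASI-75, so the claim reproduces.

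**Critical value.** With df = 1 the SAP's formula is WH = (CMH^(1/3) − 7/9) / sqrt(2/9). A reported p of 0.05 corresponds to WH = 1.6449, so

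CMH = (7/9 + 1.6449 × 0.4714)^3 = (0.7778 + 0.7754)^3 = 1.5532^3 = 3.747.

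The correct 1-df critical value is 3.841.

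**Asymptotic size.** P(chi-square(1) > 3.747) = 0.0529. At other nominal levels:

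| Nominal level | Actual size |
|---|---|
| 0.05 | 0.0529 |
| 0.025 | 0.0264 |
| 0.01 | 0.0103 |
| 0.005 | 0.0049 |
| 0.001 | 0.00084 |

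The error changes sign between 0.01 and 0.005. At nominal 0.05 it shrinks with df: 5.29% at df = 1, 5.14% at df = 2, 5.09% at df = 3.

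**Effect on a borderline result.** At CMH = 3.8415 (p = 0.0500), the cube root is 1.5661, WH = (1.5661 − 0.7778)/0.4714 = 1.672, and the reported p is 0.0472.

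**Finite-sample check.** The null was simulated with N = 225, 2:1 allocation, 12 strata, 25 imputations and Rubin's rules. One set of runs (20,000 per case) gave 5.0 to 5.3% for the SAP's rule and 4.6 to 5.0% for a pooled signed root. A separate set at a 13% null rate (30,000 per case with missing data, 200,000 without) gave 5.1 to 5.6% against 4.9 to 5.3%. The absolute rates move with the assumptions and with simulation error. The excess on the same data is stable, at about 0.2 to 0.35 points.

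**Chance that it matters for the primary endpoint.** The pooled rate is (150 × 0.38 + 75 × 0.13)/225 = 0.2967. The null standard error is sqrt(0.2967 × 0.7033 × (1/150 + 1/75)) = 0.0646, so Z has mean 0.25/0.0646 = 3.87. The standard error under the alternative is sqrt(0.38 × 0.62/150 + 0.13 × 0.87/75) = 0.0555, so Z has SD 0.0555/0.0646 = 0.859. The affected band is Z from sqrt(3.747) = 1.936 to sqrt(3.841) = 1.960. Its probability is Φ(−2.22) − Φ(−2.25), about 0.1%.

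**The p-value rule.** Appendix 3 halves the two-sided p-value when the t statistic is positive, and gives the same instruction otherwise. Read literally, with identical imputations and CMH = 0, WH = −(7/9)/0.4714 = −1.650 and the reported p is 0.0495. A negative WH reaches p < 0.05 only if CMH < (0.7778 − 0.7754)^3, about 1.4 × 10^-8, which has probability of about 0.0001. The size barely changes, but the text is wrong.

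**The case against.** The method is a published one that the SAP cites, and the SAP calls the normality approximate. The excess is comparable to the ordinary finite-sample error of an asymptotic CMH test at this sample size. It almost never changes a decision. All of that stands, and it limits the importance of the point. It does not remove the miscalibration, which comes from the formula itself and disappears if the formula is replaced.

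Four stronger readings are tempting, and the documents do not support them.

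- *The trial's true size is 5.3%.* That figure is asymptotic and assumes that the imputed data sets agree. With imputation the size depends on a missing rate that the documents do not give.
- *Reporting a one-sided p-value doubles the error rate.* The upper tail of a chi-square statistic already covers both directions, so comparing this p-value with 0.05 is the intended two-sided test.
- *Every binary endpoint is tested anti-conservatively at every step.* The direction reverses at 0.005 and below. The gatekeeping figures are not shown in the text available, so the local alphas cannot be checked.
- *The transform loses the direction of effect.* The General Association statistic is unsigned before any transform, and direction is reported through the risk difference and odds ratio.

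**Conclusion.** The concern holds as a small calibration defect. At nominal 0.05 the stated rule rejects at CMH above 3.747 instead of 3.841, an asymptotic size of 0.0529. In simulation the excess over a correct 1-df test was about 0.2 to 0.35 percentage points.

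The critical value and asymptotic size follow from the SAP's formula and df = 1 alone. The simulated excess rests on assumed stratum sizes, missing rates of 0 to 20%, and a simple within-arm binary imputation in place of the SAP's multivariate normal model.

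A reader might infer that the primary conclusion is at risk. It is not, at the planned effect: about one trial in a thousand would land in the affected band. The documents state no power for the major secondary endpoints other than EASI-75 (which is co-primary for the EMA), so a borderline result there is the more plausible case. The change is worth making because it is cheap and restores the stated level, not because the analysis is invalid.

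**What to change.** In the CMH Test part of Appendix 3, replace the transform and the p-value rule with the following:

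1. In each imputed data set, compute Z = sign(Mantel-Haenszel risk difference) × sqrt(CMH). Both ingredients are already produced there.
2. Pool Z with standard error 1 in PROC MIANALYZE.
3. Report its ordinary two-sided p-value.

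With 1 df, the two-sided test of this Z in a complete data set is exactly the chi-square test of the CMH statistic, so no approximation is added. The one-sided p-value rule with its two identical branches is no longer needed.

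State that the tipping-point analysis (SAP 6.4.2) uses the same statistic. Its extreme cells take a single-data-set p-value while the others are pooled. If that pooling follows Appendix 3, the significance threshold currently shifts within one grid for reasons unrelated to missing data.

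Do not take the p-value from the pooled Mantel-Haenszel risk difference instead. Under the null it rejected 5.4 to 5.6% in one set of simulations without missing data and 5.0 to 5.4% in another, no better than the rule it would replace. It would also swap the protocol's CMH test for a Wald test.

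The programming cost is about one line. Borderline p-values become slightly less favourable. The larger cost is procedural. SAP Version 4 followed primary database lock, when a limited number of study-team statisticians had been unblinded. A change to the primary p-value at that stage must be justified, and documented as made by statisticians blinded to the data.

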For assessments of the primary endpoints and other binary efficacy and health outcomes endpoints, the following will be provided:

- Crude proportions for each treatment group along with the 95% two-sided asymptotic (that is, not continuity corrected) confidence intervals (CIs).
- The estimated common risk difference along with 95% CIs. The common risk difference is the difference in proportions adjusted for the stratification factors as mentioned in Section 6.3. SAS PROC FREQ will be used for the estimates and CIs, where the CIs are calculated by using Mantel-Haenszel-Sato method (Sato 1989).
- Cochran-Mantel-Haenszel (CMH) test will be used to compare the treatment groups while adjusting for the stratification factors. The CMH p-value will be reported, and the CMH adjusted odds ratio along with the 95% two-sided asymptotic (that is, not continuity corrected) CIs.

Treatment comparisons of key continuous efficacy variables and health outcome variables at each postbaseline time point will be made using analysis of covariance (ANCOVA) with the following in the model: treatment group, baseline value, and stratification factors mentioned in Section 6.3. Type III tests for least squares (LS) means will be used for statistical comparison between treatment groups. The LS mean difference, standard error, p-value, and 95% CI, unless otherwise specified, will also be reported.

Treatment comparisons of other continuous efficacy variables and health outcome variables with multiple postbaseline measurements will be made using mixed-model for repeated measures (MMRM). When MMRM is used, the model includes treatment, baseline value, visit, the interaction of the baseline value-by-visit, the interaction of treatment-by-visit, and the stratification factors mentioned in Section 6.3 as fixed factors. The covariance structure to model the within-patient errors will be unstructured. If the unstructured covariance matrix results in a lack of convergence, the heterogeneous Toeplitz covariance structure, followed by the heterogeneous autoregressive covariance structure will be used. The restricted maximum likelihood (REML) will be used. The Kenward-Roger method will be used to estimate the denominator degrees of freedom. Type III tests for the LS means will be used for the statistical comparison; the 95% CI will also be reported.

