#### **6.4.1. Primary Analysis - Markov Chain Monte Carlo Multiple Imputation (MCMC-MI)**

The primary method of handling missing efficacy data relative to the primary estimand will be as follows for both binary and continuous endpoints:

For patients who receive rescue medication (high-potency TCS or systemic AD treatment, defined in [Appendix 2](#)) or discontinue treatment due to lack of efficacy, set to the patient's baseline value subsequent to this time through Week 16. The MCMC-MI will be used to handle the remaining missing data. Imputation will be conducted within each treatment group independently so the pattern of missing observations in one treatment group cannot influence missing value estimations in another. The SAS PROC MI with the MCMC option will be used to conduct the MCMC-MI. The imputation model will include the relevant baseline and postbaseline.

For each imputation process, 25 datasets with imputations will be calculated. The initial seed values are given in [Table KGAD.6.6](#). Each complete data set will be analyzed with the specified analysis. The results from these analyses will be combined into a single inference using SAS PROC MIANALYZE.

Cochran-Mantel-Haenszel (CMH) test statistic will be transformed using the Wilson-Hilferty transformation and then standardized (Ratitch 2013) prior to combining them using SAS PROC MIANALYZE. Details of combining estimates and test statistics for categorical endpoints with multiple imputation can be found in [Appendix 3](#).

For binary responses related to EASI and IGA, the binary response variables will be calculated based on the multiply imputed datasets that have been created. Because the MCMC algorithm is based on the multivariate normal model, imputed values for IGA will not generally be one of the discrete values used in IGA scoring (0, 1, 2, 3, or 4). Therefore, to derive the binary IGA response variable, standard rounding rules will be applied to the imputed values. For example, if a patient has an IGA score imputed as 1.4 (and assuming a Baseline IGA score of 3), the imputed value would be rounded down to 1, and the minimum change from Baseline of 2 would have been met. This patient would be considered a responder.

For derivation of an EASI-75 and EASI-90 response, no rounding will be performed. The imputed Week 16 EASI value will be compared directly to the observed Baseline EASI value to determine whether a reduction of at least 75% or 90% was achieved.

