**Table KGAD.6.9. Description of Efficacy/Health Outcome Analyses**

Measure	Variable	Analysis Method (Section 6.1)	Population (Section 6.1.1)	Comparison/Time Point	Analysis Type
Investigator’s Global Assessment (IGA)	Proportion of patients achieving IGA [0,1] with a $\geq 2$ -point improvement	CMH analysis with MCMC-MI	mITT	Leb 250 mg Q2W vs PBO; Week 16 and all scheduled visits in Treatment Period	Primary analysis: W16; Secondary analysis: other timepoints
		CMH analysis with NRI	mITT	Leb 250 mg Q2W vs PBO; Week 16 and all scheduled visits in Treatment Period	Supplementary analysis
		CMH analysis with tipping point analysis	mITT	Leb 250 mg Q2W vs PBO; Week 16	Sensitivity analysis
	Proportion of patients achieving IGA [0]	CMH analysis with NRI	mITT	Leb 250 mg Q2W vs PBO; Week 16 and all scheduled visits in Treatment Period	Secondary analysis
	Proportion of patients achieving both IGA [0,1] with a $\geq 2$ -point improvement and a $\geq 4$ -point improvement in Pruritus Numeric Rating Scale (NRS)	CMH analysis with MCMC-MI	mITT with Baseline Pruritus NRS score at least 4	Leb 250 mg Q2W vs PBO; Week 16 and all scheduled visits in Treatment Period	Secondary analysis
CMH analysis with NRI		mITT with Baseline Pruritus NRS score at least 4	Leb 250 mg Q2W vs PBO; Week 16 and all scheduled visits in Treatment Period	Secondary analysis	
Eczema Area and Severity Index (EASI)	Change from baseline in EASI score	ANCOVA with MCMC-MI	mITT	Leb 250 mg Q2W vs PBO; Week 16 and all scheduled visits in Treatment Period	Secondary analysis: percent change Week 16
	Percent change from baseline in EASI score	MMRM	mITT	Leb 250 mg Q2W vs PBO; Week 16 and all scheduled visits in Treatment Period	Secondary analysis

Description of Efficacy/Health Outcome Analyses

Measure	Variable	Analysis Method (Section 6.1)	Population (Section 6.1.1)	Comparison/Time Point	Analysis Type
	Proportion of patients achieving EASI-75	CMH analysis with MCMC-MI	mITT	Leb 250 mg Q2W vs PBO; Week 16 and all scheduled visits in Treatment Period	Primary analysis: EASI-75, W16; Secondary analysis: EASI-90, W16; Secondary analysis: other timepoints
	Proportion of patients achieving EASI-90				
	CMH analysis with NRI				
		CMH analysis with tipping point analysis	mITT	Leb 250 mg Q2W vs PBO; Week 16	Sensitivity analysis
	Proportion of patients achieving EASI-50	CMH analysis with MCMC-MI	mITT	Leb 250 mg Q2W vs PBO; Week 16 and all scheduled visits in Induction Period	Secondary analysis

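### As written, both branches of SAP Appendix 3's pooled CMH p-value rule are the same, so whenever the pooled t is negative the reported p is 1 minus its intended value

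*SAP*

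**What the plan says.** Appendix 3 of the SAP sets out how results from the 25 imputed datasets are combined, and its scope is given as "Following the implementation of Markov Chain Monte Carlo multiple imputation (MCMC-MI) imputation as specified in Section 6.4.1". Section 6.4.1 says of the CMH result that the "test statistic will be transformed using the Wilson-Hilferty transformation and then standardized", and refers to Appendix 3 for the detail.

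Under CMH Test, the appendix gives each transformed statistic a standard error of 1 and pools them with PROC MIANALYZE. It does not use the two-sided p-value from that procedure directly. Instead, "the 1-sided p-value is computed manually using both the t statistic and 2-sided p-value output by PROC MIANALYZE". The two branches are then:

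- t positive: "if t statistic is >0, then the 1-sided p-value is computed as one half of the 2-sided p-value"
- all other cases: "otherwise, the 1-sided p-value is computed as one half of the 2-sided p-value"

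The paragraph ends: "The resulting 1-sided p-value is reported as the pooled p-value for the CMH test". No other place in the SAP or protocol gives a different rule for t at or below zero.

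Table KGAD.6.9 plans CMH with MCMC-MI for IGA 0/1, the EASI responses, Pruritus NRS, Sleep-loss, DLQI and the composites. The time points for IGA 0/1, for example, are "Leb 250 mg Q2W vs PBO; Week 16 and all scheduled visits in Treatment Period". Section 6.1.2 puts the p-value beside the effect estimates: "The CMH p-value will be reported, and the CMH adjusted odds ratio along with the 95% two-sided asymptotic". It also asks for the common risk difference with its interval.

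**The concern.** The Wilson-Hilferty value increases with the CMH statistic. A large positive value means the arms differ, and a negative value means they are close. A negative value does not mean that placebo did better. The p-value for the two-sided treatment comparison is therefore the upper-tail area, and the one-sided label in the appendix is not a fault in itself.

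The sign of t has to be checked because halving the two-sided p gives the upper tail only when t is positive. When t is negative, halving gives the lower tail, and the upper tail is 1 minus that. With both branches identical, the sign check does nothing and the lower tail is reported.

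A programmer or independent validator who follows the text literally would produce wrong p-values for comparisons with little or no difference. One who follows the evident intent would depart from the approved SAP. In the first case a reader could see a p-value that looks like a trend beside an odds ratio near 1.

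**Working it through.** The plan gives no numerical p-value for this rule, so the rule itself was computed.

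**Inputs.** The transformation, the standard error of 1 and the branch rule come from Appendix 3 (CMH Test). The 25 imputations come from Section 6.4.1. The 150:75 allocation and the planned rates (38% vs 13% for IGA, 58% vs 20% for EASI-75) come from SAP Section 5.2. Appendix 3 uses the General Association statistic, which has 1 degree of freedom for two arms and a binary outcome (derived, not stated).

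**Formula with df = 1.** WH = (CMH^(1/3) − 7/9) / √(2/9).

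- Printed rule: p = p₂/2 always.
- Upper tail: p = p₂/2 if t > 0, otherwise 1 − p₂/2.
- For t < 0 the two sum to exactly 1. This identity needs no assumption about strata, missing data or effect size.

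**Where the sign changes.** WH = 0 at CMH = (7/9)³ = 0.4705, and P(χ²₁ < 0.4705) = 0.507. At 150:75 this corresponds to a difference of √0.4705 × √[p(1−p)(1/150 + 1/75)]. That is 0.686 × 0.0476 = 3.3 points at 13% response and 0.686 × 0.0612 = 4.2 points at 25%.

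**One dataset, no between-imputation variance.** For example, CMH = 0.01 gives (0.2154 − 0.7778)/0.4714 = −1.193.

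| CMH | t | p, printed rule | p, upper tail | untransformed χ² p |
|---|---|---|---|---|
| 0 | −1.650 | 0.0495 | 0.9505 | 1.000 |
| 0.01 | −1.193 | 0.1165 | 0.8835 | 0.920 |
| 0.05 | −0.868 | 0.193 | 0.807 | 0.823 |
| 0.10 | −0.665 | 0.253 | 0.747 | 0.752 |
| 0.30 | −0.230 | 0.409 | 0.591 | 0.584 |
| 1 | 0.471 | 0.319 | 0.319 | 0.317 |
| 3.841 | 1.672 | 0.047 | 0.047 | 0.050 |

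The upper-tail column follows the χ² p-value approximately. The printed rule does so only when t > 0.

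**With pooling.** Take a mean transformed statistic of −1.2 and between-imputation variance 0.2. The total variance is 1 + (1 + 1/25) × 0.2 = 1.208, so t = −1.2/√1.208 = −1.092 and p₂ = 0.275. The printed rule gives 0.138 and the upper tail 0.862.

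**Floor.** The transformed value cannot go below −1.650 and the pooled variance cannot be less than 1. With t ≤ 0 the printed p therefore cannot fall below 0.0495. In a single dataset, a false p < 0.05 needs CMH below about 1.4 × 10⁻⁸.

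**How often, under no effect.** Simulations used 150:75, 12 strata, response 13% or 25%, 5–10% missing, 25 imputations and 4000 trials per setting.

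- t ≤ 0 occurred in 48.7–49.8% of trials.
- In those trials the median reported p was 0.28–0.31 instead of 0.69–0.72, and the smallest was 0.085–0.136.
- Rejections at 0.05 were identical under both rules (5.1–5.4%).

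A separate unstratified simulation (8% missing, 20,000 trials per setting) gave t ≤ 0 in 50–51% and 5.2% rejections under both rules.

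**At the planned effects.** Exact binomial enumeration on complete, unstratified data gives P(CMH < 0.4705) = 0.00017 for 38% vs 13% and 0.0000002 for 58% vs 20%.

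**At small by-visit effects (assumed).** The simulated share with t ≤ 0 was 34% at 18% vs 13%, 25% at 10% vs 5%, and 40% at 5% vs 3%. Across all nine stratified settings, one rejection changed: 1 of 4000 trials at 5% vs 3%, with reported p = 0.0495.

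**The case against.** The strongest reply is that this is a missing "1 minus" and not a choice of method. The appendix says the sign of t is used, which makes sense only if the branches differ, so the code may well be right. That stands: only the SAP text is established, and the consequence holds if the code follows it.

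It is also fair that no planned inference turns on this. The gatekept endpoints are all at Week 16. At the planned primary effects a negative t is very rare, and rejection rates agree under both rules. The one changed rejection sits at the mathematical floor and carries no weight.

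The figure of 0.12 is a single-dataset value and is not typical. After pooling, a result with t ≤ 0 and reported p below 0.15 occurred in 2.5% of null trials (13% response, 5% missing) and 0.05% (25% response, 10% missing). The usual misreport is about 0.3 for a value near 0.7, and a reader would call both non-significant.

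There are cross-checks as well. The pooled risk difference and odds ratio do not use this rule. For IGA 0/1, Pruritus NRS and the composites, Table KGAD.6.9 also plans non-responder imputation, which needs no pooling. Finally, the repaired p-value is itself an approximation: 0.8835 against 0.920 at CMH = 0.01.

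These points limit the weight of the error. They do not make the written rule usable: it is the only rule the SAP gives for this p-value, and it covers the primary analysis.

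**Conclusion.** The concern holds for the SAP as written. For every MCMC-MI binary comparison with a negative pooled t, Appendix 3 returns 1 minus the intended p. That is about half of comparisons with no true difference, and roughly a quarter to two-fifths at the small by-visit effects assumed here. Reported values are capped at 0.5 and move the wrong way as the arms converge.

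Results with t > 0 are unchanged, and the primary, co-primary and gatekeeping decisions are practically unaffected. The harm is misreported non-significant p-values that contradict the estimates beside them. It should be fixed, but it does not threaten the trial's main conclusions.

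The identity p(printed) = 1 − p(intended) is exact. The frequencies rest on assumptions the documents do not supply: strata mix (region 45/45/10%, 22% adolescents, 30% IGA 4), missing rates of 5–10%, and the by-visit response rates.

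**What to change.** In Appendix 3, CMH Test, make the second branch return 1 minus half of the two-sided p-value, and check the SAS code against the corrected text. If the code followed the printed rule, re-issue the affected by-visit p-values. Section 6.4.2 also pools CMH results through PROC MIANALYZE but does not cite Appendix 3. If the tipping-point p-values are derived in the same way, the corrected rule should apply there too.

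The cost is one clause and a check of one line of code. The correction only replaces p-values at or below 0.5 with values at or above 0.5, so it cannot move any result towards significance.
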